3. RATIONALE

3.1 Rationale for Radiotherapy in Treatment of Pancreatic and Periampullary Adenocarcinomas

Radiation therapy is a widely accepted treatment for pancreatic cancer. The Gastrointestinal Tumor Study Group (GITSG) carried out a series of landmark studies demonstrating the effectiveness of radiation therapy as both adjuvant and definitive treatment in pancreatic cancer (6,7). Modern radiation treatments have increasingly used conformal fields and dose escalation to enhance tumor control (8, 9). Efforts to increase radiation dose to the pancreatic tumor without risking normal tissue injury have generally required relatively invasive techniques such as interstitial implantation of radioactive metals or intraoperative radiotherapy (IORT) (10, 29). Historically, the local control rates for conventionally fractionated radiotherapy have ranged from 25-50%. Local progression of pancreatic cancers can result in considerable morbidity, including gastric outlet obstruction, biliary obstruction, and pain (30).

Periampullary tumors are also frequently treated with radiation therapy. Patients with periampullary tumors have also been included in this trial because of anatomic and

pathological similarities to patients with pancreatic cancer and the fact that the treatment paradigm for these cancers is similar to pancreatic cancer. Patients with periampullary tumors also have similar survival and recurrence patterns as patients with pancreatic cancers (31). Periampullary adenocarcinoma is a rare malignancy, comprising less than 1% of all digestive cancers and occurring at an annual age-adjusted incidence of only 0.3 cases per 100,000 individuals (32). As a consequence of this low prevalence, few studies have been performed in this population, and patients who fail definitive therapy (surgical resection in association with neoadjuvant or adjuvant CRT/chemotherapy for resectable disease; conventional CRT or chemotherapy for unresectable disease) have limited options for further treatment (33,34). Unfortunately, even among patients with resectable periampullary adenocarcinoma, over 50% will recur following definitive treatment (35). This trial, therefore, seeks to study SBRT as a means of providing patients with periampullary tumors with an additional treatment option in the case of locally recurrent or progressive disease.

3.2 Rationale for Fractionated Stereotactic Radiotherapy

The mortality rate for pancreatic cancer approaches 100%. Current therapies provide only partial palliation of symptoms and slight prolongation of survival. More effective therapies are clearly needed. Several clinical trials have shown that Linac based SBRT has the potential to significantly improve progression-free survival of patients with pancreatic tumors, which could translate into both more effective palliation and longer patient survival.

Koong *et al.* previously used the CyberknifeTM stereotactic radiosurgery system to demonstrate that a single dose of 25 Gy Linac based stereotactic body radiotherapy (SBRT) was feasible for patients with locally advanced pancreatic cancer (36). Furthermore, this dose of radiation resulted in near 100% progression free survival and effectively palliated symptoms related to the local growth of pancreatic tumors. Based on this study, the same group also completed a phase II study assessing the efficacy of combining a standard five-week course of chemoradiotherapy followed by a stereotactic radiosurgery boost to the primary tumor in patients with locally advanced pancreatic cancer. In this cohort of 19 patients, 100% of tumors were without local progression. However, all patients eventually developed metastases, with a median time to progression of 5.5 weeks.

More recently, another phase II study treated locally advanced pancreatic cancer patients with gemcitabine followed by 25 Gy of Linac based SBRT delivered with Cyberknife and maintenance gemcitabine chemotherapy. In this study, the excellent progression free survival was confirmed from previous studies (81%). The median overall survival was 11.4 months, median time to progression was 9.7 months and the 1 year survival was 50% (37). There were no significant acute GI toxicities however, of the 15 patients alive >6 months after Linac based SBRT, 7 (47%) experienced Grade 2 or greater GI toxicity, with 2 (13%) of the 15 experiencing Grade 3 or greater GI toxicity.

Linac based SBRT is delivered using linear accelerators and image-guided radiation therapy (IGRT). These machines combine a conventional high-energy linear accelerator with a kV imager capable of volumetric, cone beam CT (CBCT). Because of these innovations, it is possible to deliver highly accurate, stereotactic radiation treatments.

A recent protocol evaluated full dose gemcitabine before and after single fraction Linac based SBRT. Preliminary results indicate that the local progression free survival was comparable to what was previously observed (90%) with CyberKnife treatment (personal communication). All acute toxicity was grade 2 or less; however, a minority of patients developed late duodenal ulcers (15%), including 1 perforation (5%) with a single fraction of Linac based SBRT. Therefore, LInac based SBRT appears to achieve local control of

pancreatic tumors in a large majority of patients with reasonable rates of toxicity, suggesting that Linac based SBRT would be an effective treatment option for patients with locally recurrent disease, as we propose in this protocol.

To date, Stanford has treated more than 150 patients with Linac based SBRT, and this treatment has resulted in local control rates of >90% with acceptable acute GI toxicity. We predict that this treatment will not adversely impact patients' quality of life. Although QOL measures have not been thoroughly studied among pancreatic cancer patients treated with Linac based SBRT, the majority of patients treated with Linac based SBRT appear to derive a clinical benefit as assessed by decreased pain, decreased fatigue, and increased weight. A single fraction of Linac based SBRT (25 Gy x 1) has resulted in excellent tumor control. However, close to 50% of these patients developed late duodenal toxicity within one year, primarily because of the proximity of the duodenum to the pancreas.

We hypothesize that delivering fractionated Linac based SBRT (5 Gy x 5 or 6.6 Gy x 5) instead of single fraction treatment will result in equivalent tumor control with less late toxicity ($\leq 20\%$). At this time, there is no clear consensus regarding an optimal fractionation schedule for unresectable pancreas cancer (38,39). Based on a recent study, this fractionation schedule is predicted to provide equivalent tumor control probability to 25 Gy x 1 while resulting in less normal tissue toxicity (40).

Although we believe this schedule (5 Gy x 5 or 6.6 Gy x 5) will result in good tumor control and acceptable toxicity, the potential clinical efficacy of this short-course, hypofractionated regimen is unknown. The choice of this regimen as a potentially effective approach for unresectable pancreatic cancer treatment is based on three observations. First, a similar schedule (5 Gy x 5) has been widely and efficaciously used in the neoadjuvant setting for rectal cancer, although a much larger field is used. Additionally, a series of patients with resectable pancreatic lesions treated at the M.D. Anderson Cancer Center strongly suggest that a 5-FU based chemoradiation regimen consisting of 30 Gy in 10 fractions over 2 weeks reduces treatment time and toxicity compared with a regimen consisting of 50.4 Gy in 28 fractions over 5 to 6 weeks without compromising overall survival or local control. Hong et al. from Massachusetts General Hospital have reported on a neoadjuvant regimen delivering 5 Gy x 5 to the pancreatic tumor plus adjacent lymph nodes using proton beam radiation (41). They show this regimen to be safe, with no instances of dose limiting toxicity observed and only 4 of 15 patients developing grade 3 toxicity (no patients experienced grade 4 toxicity). The phase I feasibility study outlined in this protocol proposes a 5 Gy x 5 (patients who previously received radiotherapy) or 6.6 Gy x 5 (radiation-naïve patients) fractionation schedule treating the region of local recurrence or unresectable pancreatic tumor plus a 3 mm margin. These volumes will be substantially smaller than the regimens outlined above for rectal and pancreatic cancer, likely leading to a lesser degree of toxicity. Using the linearquadratic formulation, the biologically equivalent dose (BED) of the two proposed fractionation schedules are given in comparison to other commonly used schemes (table 1). While the BED for the 5 Gy x 5 schedule (early/late 37.5/66.7) must necessarily be lower because it will be used in patients who have already been treated with radiation to the pancreatic region, that of the proposed 6.6 Gy x 5 schedule (BED early/late 54.8/105.6) closely approximates that of standard chemoradiation (BED early/late 60/83.3), but without concurrent chemotherapy and treating a smaller tumor margin (0.3 cm vs. ~ 2 cm). Furthermore, the proposed 6.6 Gy x 5 fractionation schedule has a much lower late BED (105.6 vs. 233.3) with a similar early BED (54.8 vs. 87.5) as the previous 25 Gy x 1 regimen.

Table 1:

	NodesTx	Chemo	BED early	BED late
			a/b=10	a/b=-3
50.4	Yes	Yes	60	83.3
30 Gy/10	Yes	Yes	39	60
25 Gy/5	No	No	37.5	66.7
33 Gy/5	No	No	54.8	105.6
25 Gy/1	No	No	87.5	233.3

In this study, we will refine our current understanding of radiation tolerance of the pancreas and adjacent organs, thereby making it possible to treat future patients more safely and aggressively.

The major benefit of Linac based SBRT/chemotherapy for unresectable, locally recurrent and locally progressive pancreatic and periampullary tumors is improved local control and palliation of symptoms related to local progression of these tumors. In addition, radiosurgical ablation of the tumor at the primary site can theoretically prevent distant seeding from the pancreatic tumor itself. Ultimately, these improvements in the treatment of pancreatic and periampullary cancer may translate into an improved quality of life and overall survival.

Quality of life will be assessed using the European Organization for Research and Treatment in Cancer quality of life core cancer questionnaire with the pancreatic cancer module (EORTC QLQ-C30/PAN26). The EORTC QLQ-C30 is a multidimensional, 30-item questionnaire, which assesses five functional scales (physical, role, cognitive, emotional, and social), three symptom scales (fatigue, pain, and nausea/vomiting), a global health/QOL scale, as well as 6 single items (42). The EORTC QLQ-PAN26 supplements the core questionnaire with 26 items specific for patients with pancreatic cancer (43,44). These instruments have been validated in patients receiving treatment for metastatic and resected pancreatic cancer and are sensitive to identify treatment related changes in quality of life. The quality of life of patients in this study will be compared to historical cohorts of patients treated with conventional chemoradiation at Johns Hopkins.

3.3 Rationale for Use in Treatment of Locally Progressive or Recurrent Disease

The development of recurrent pancreatic cancer after definitive treatment with surgery, radiation, chemotherapy, or a combination of these universally portends a dismal prognosis, with the 5-year survival for such patients being 5.6% or less (45). Unfortunately, this scenario is not uncommon; even among the small number of patients (10-15%) able to undergo potentially curative surgical resection, more than 80% subsequently develop recurrent disease (46). Among the majority of patients with pancreatic cancer who present with unresectable disease, chemoradiation is able to transiently stabilize the disease in some patients and to prolong median survival to 8-14 months (47-50). However, virtually 100% of patients develop disease progression and succumb within 3 years (51-55).

The pattern of recurrence in pancreatic cancer is well known (11,18,56,57) and is similar to that of periampullary adenocarcinoma (35). Following resection, 71-77% develop distant metastases within 2 years, often accompanied by concurrent locoregional recurrence, while up to 30% (58, 59) exhibit isolated locoregional recurrence (60,61). Patients who develop combined distant/locoregional recurrence have a median survival of 3 months from the time

of recurrence, while those with isolated locoregional recurrence have a median survival of 7 months (60). Locoregional recurrence is, therefore, a common and serious problem both in the setting of metastatic disease and as an isolated entity. Symptomatic manifestations include pain, gastric outlet/small bowel obstruction, portal hypertension, biliary obstruction, and malnutrition (61). Although survival is determined chiefly by systemic disease control, local control is an important factor contributing to quality of life (62,63). The symptoms associated with local recurrence require a mode of treatment that is swift and efficacious in order to restore patient quality of life and give patients the best chance at greater overall survival.

To date, no studies involving radiotherapy have been performed that primarily focus on this specific population of patients who have developed local failure after previous standard of care or protocol therapy for pancreatic or periampullary adenocarcinoma. Consequently, no standard treatment option has yet been defined. Current options include surgical re-exploration with possible re-resection, palliative chemotherapy or conventionally fractionated chemoradiotherapy (CRT), and best supportive care. Each of these has significant drawbacks, including: high degree of invasiveness and morbidity in the case of surgical re-resection (41,64); slow onset of effect, substantial systemic toxicity, and inferior local control rates (71.1%) with palliative chemotherapy or conventionally fractionated CRT (65); and lack of efficacy and diminished overall survival with best supportive care alone.

We propose that the drawbacks associated with the current treatment options above can be circumvented or mitigated by the use of fractionated SBRT, while simultaneously achieving excellent rates of local control and symptom palliation. Linac based SBRT is a non-invasive means of achieving effective local control in a large majority of patients (81 to nearly 100% at one year in previous studies) (36,37,66,67). Additionally, we propose to deliver the Linac based SBRT in 5 fractions over the course of 1-2 weeks, allowing for swift alleviation of symptoms associated with local tumor recurrence/progression. Conventionally fractionated radiation therapy (RT), on the other hand, delivers a similar BED (see table 1 in section 3.2) over a much longer period of 5-6 weeks. Furthermore, the tighter margins used in Linac based SBRT (0.2-0.3 cm) compared to conventional RT (2-3 cm) may result in less gastrointestinal toxicity (68). Therefore, we suggest that Linac based SBRT avoids the drawbacks associated with other existing treatment options for patients with recurrent pancreatic adenocarcinoma; that is, Linac based SBRT is effective, non-invasive, swift to take effect, and associated with a relatively mild toxicity profile.

Two recent studies support this assertion. In 2009, Chang *et al.* reported on the use of Linac based SBRT delivered as 25 Gy in a single fraction for patients with unresectable pancreatic adenocarcinoma (67). Of the 77 patients, 58% had locally advanced disease and 14% had medically inoperable disease, but the remainder were similar to our population in that they had either low-burden metastatic disease (19%) or locally recurrent disease (8%). Results were encouraging, with rates of freedom from local progression at 6 and 12 months of 91% and 84%, respectively. Overall survival at 6 and 12 months was 56% and 21%, respectively. Only 5% of patients experienced grade 2 or greater acute toxicity, 4% experienced grade 2 late toxicity, and 9% experienced grade 3 or greater late toxicity. Rates of grade 2 or greater late toxicity were 11% and 25% at 6 and 12 months, respectively.

In 2010, Didolkar *et al.* reported on the use of Linac based SBRT doses ranging from 15 to 30 Gy delivered in 3 equal fractions, with mean dose of 25.5 Gy over 3 days (66). Eighty-five patients were studied; the majority (71 patients) had locally advanced disease, but a small number (14 patients) were included who were similar to our population in that they had locally recurrent disease. Results were again encouraging, with 78 patients (92%) achieving complete response, partial response, or stable disease for a duration of 3-36 months with a

median of 8 months. Pain relief was noted in the vast majority of patients lasting for 18-24 weeks. Median survival from time of Linac based SBRT was 8.65 months, which is comparable to or better than reported results for locally advanced pancreatic cancer (69-72). Nineteen patients (22.4%) developed grade 3-4 gastrointestinal toxicity, consisting of duodenitis, gastritis, and diarrhea in order of decreasing frequency. One patient developed renal failure.

We recently presented the preliminary results of our phase II multi-center trial of gemcitabine (GEM) and fractionated Linac based SBRT to determine if a high rate of LPFS with reduced toxicity could be achieved. After multidisciplinary review, 32 pts with locally advanced PDA received GEM in sequence with Linac based SBRT (6.6 Gy in 5 consecutive daily fractions, 33 Gy total). LPFS, metastasis free survival (MFS), and overall survival (OS) were measured from date of tissue diagnosis. Objective tumor response (OTR) was assessed by RECIST/PERCIST. EORTC QLQ-C30/PAN26 questionnaires were used to measure QOL. Median f-up was 12 mos (range, 2-23). Mean age was 69.9 yrs (SD, 9.8) and 62% were male. Patients received a mean of 2.2 (SD, 1.0) GEM doses prior to SBRT and 8.3 (SD, 5.6) doses total. All pts completed SBRT. Median OS was 15.9 months (95% CI, 12.7-18.8). Stratification by CA19-9 > or < 90 at diagnosis yielded a hazard ratio of 6.2 for > 90(p=0.021). Median LPFS has not been reached and median MFS was 10.2 mos (95% CI, 2.9-17.5). LPFS rate at 1 year was 87%. OTR on CT was seen in 41%, while 41% had stable disease and 18% progressed. Tumor metabolic activity decreased in 17/18 patients with pre/post- Linac based SBRT PET available. Mean peak SUV was 4.0 pre- Linac based SBRT versus 2.4 post-Linac based SBRT (p=0.002). Median CA19-9 was reduced from 124.7 prior to SBRT to 43.9 afterwards. Acute toxicity included: grade 2 anorexia (37%), fatigue (28%), nausea (22%), abd pain (19%), weight loss (9%), diarrhea (3%); gr 3 nausea (9%); and gr 4 nausea (6%). Late gr \geq 3 GI toxicity was seen in 9%. Mean QOL score 4 wks post-Linac based SBRT was similar to baseline (p=0.38). At 6 most here was a trend towards improved QOL (p=0.07). Overall, fractionated Linac based SBRT with GEM achieved high rates of LPFS and tumor response. Minimal grade ≥ 3 acute and late toxicity was observed. Linac based SBRT is more likely to benefit patients with Ca-19-9 <90. A combination of Linac based SBRT with more aggressive chemotherapy may further improve outcomes.

Considering the difficulty of surgical re-exploration due to extensive adhesions after previous resection, the risks of surgery and general anesthesia for patients who often have impaired performance status, and the prolonged time course and inferior local control associated with conventional CRT, we propose that SBRT may be a viable alternative treatment option for patients who have failed other modes of therapy through local recurrence or local progression. The paucity of studies focusing on this population and lack of a standardized treatment paradigm for these patients underscore the need for further investigation. The recent studies delineated above suggest that Linac based SBRT is a safe and promising therapeutic option for pancreatic and periampullary cancers that merits further study in the specific patient population that will be treated using this protocol.

4. PATIENT SELECTION

4.1 Inclusion Criteria

- 4.1.1 Age \geq 18 years.
- 4.1.2 Karnofsky Performance Status \geq 70% (see Appendix II).
- 4.1.3 Histologically confirmed adenocarcinoma of the pancreas or ampulla of Vater; at least the majority of the histopathologic specimen must be identified as adenocarcinoma as opposed to another histologic subtype.

*If histological confirmation of adenocarcinoma cannot be obtained by biopsy, the following procedures may be employed:

- 4.1.3.1 Attempt a repeat biopsy to obtain a diagnosis.
- 4.1.3.2 Present the case at JHU tumor board and if the candidate has one of the following: a rising CA 19-9 or radiographic evidence of recurrence on MRI, CT, and/or PET scan then the patient can be considered for treatment on protocol.

However, if these objectives cannot be met, the patient will not be a candidate.

- 4.1.4 Pancreatic or periampullary tumors must be less than 8.0 cm in greatest axial dimension at the time of treatment planning.
- 4.1.5 Either:

Patients who have received RT: Previously (≥ 6 months before retreatment) completed treatment for pancreatic or periampullary adenocarcinoma consisting of either surgical resection with neoadjuvant/adjuvant conventional CRT for resectable disease or conventional CRT as definitive treatment for unresectable disease. These patients who have received prior radiation therapy will constitute Cohort A and will receive SBRT as 5 Gy x 5.

*patients may be receiving continued chemotherapy post initial CRT.

OR

Patients who have not received RT: Previously (\geq 3 months before retreatment) initiated treatment for pancreatic or periampullary adenocarcinoma consisting of chemotherapy alone for unresectable disease or surgical resection with neoadjuvant/adjuvant chemotherapy for resectable disease. These patients who have not received prior radiation therapy will constitute Cohort B and will receive SBRT as 6.6 Gy x 5.

*patients must have attempted chemotherapy upon initial diagnosis.

4.1.6 Patients must have acceptable organ and marrow function as defined below (within 2 weeks prior to radiotherapy):

- Leukocytes $\geq 2,000/\mu L$
- Absolute neutrophil count $\geq 1,000/\mu L$
- Platelets \geq 75,000/µL
- Total Bilirubin ≤1.5X normal institutional limits
- AST(SGOT)/ALT(SGPT) <2.5X institutional upper limit of normal
- Creatinine \leq institutional upper limit of normal

OR

• Creatinine clearance $\geq 60 \text{ mL/min}/1.73 \text{ m}^2$ for patients with creatinine levels above institutional normal

- 4.1.7 Ability to understand and the willingness to sign a written informed consent document.
- 4.1.8 Must be a patient to be treated with SBRT only at Johns Hopkins Hospital.
- 4.1.9 Life expectancy > 3 months.
- 4.1.10 Patient must be able to have fiducials placed. If not, the tumor must be posterior and adjacent to the aorta and treatment will only be permitted at the discretion of the Principal Investigator.

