8.1.1.4 Coding of specimens for privacy protection

At the time of consent, each patient will be given a specific confidential identification number (IDN). Specimens will be stored under the patient's IDN. The information can be shared with other investigators listed on this protocol. Study data will be maintained in password protected computer files (protected online database through Johns Hopkins). Only research personnel will have access to this information.

8.2 Collection of Pre and Post Treatment CT/PET Scans, Treatment Planning Scans, and Treatment Plans

- 8.2.1 Data and Image Collection
 - 8.2.1.1 Pre-Linac based SBRT PET scan is recommended but not required. Post SBRT PET scans will be optional for all patients based on the opinion of the treating physician. Pre- and post-Linac based SBRT CT scans will be mandatory for all patients (PET/CT may supplement protocol CT). All images (CT and PET) will be stored electronically by JHU through the Oncospace network and be registered to each patient using the IDN. Radiation treatment plans will also be retrospectively reviewed and stored at JHU via Oncospace. The JHU database is set up to store ROI geometries and dose distributions along with the CT. This design facilitates the investigation of dosimetric effects on tumor response and complications utilizing DVH or other attributes of the 3D dose.

For Pinnacle, the data can be directly placed in the JHU database via scripts.

- 8.2.1.2 All treatment planning scans will be stored electronically by JHU through the Oncospace network and be registered to each patient using the IDN. Specific parameters will be prospectively collected such as treatment volume and dose to adjacent structures in oncospace
- 8.2.1.3 Dynamic Whole Body PET/CT

Up to 17 patients will be recruited to a sub-project that will assess the feasibility of acquiring a quantitative dynamic whole body PET/CT early after treatment. The aim of this sub-project is to assess the extent to which dynamic PET can be used to aid in the discrimination of tumor from radiation induced inflammation in a therapy assessment setting. This could potentially enable future PET/CT-based response assessment at an earlier time than the current protocol and clinical practice, 4-6 weeks post-treatment. This will allow therapy decision (success or failure) to be made earlier and management is personalized.

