11. MEASUREMENT OF EFFECT

11.1 Anti-tumor Effect

Patients will be evaluated for anti-tumor effect by follow-up imaging (pancreas protocol CT and/or PET-CT imaging) as outlined above. All subsequent scans (post-treatment) will be compared to the same pretreatment CT or PET/CT that was used in conjunction with radiation treatment planning.

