11.1.2 Disease Parameters

Pancreatic and periampullary tumor response will be based upon standard radiographic criteria for the treated lesion and will be prospectively recorded in the JHU secure database. Radiographic response of the **pancreatic or periampullary tumor** by diagnostic CT scans will be defined **according to RECIST criteria as described below:**

CR = complete disappearance of index lesion

PR = at least 30% decrease in the longest diameter of the index lesion

PD = more than 20% increase in the longest diameter of the index lesion

SD = does not meet criteria for PR or PD

Pancreatic or periampullary tumor response will also be assessed by FDG-PET scans (when available) according to the following criteria:

CR = target lesion becomes photopenic or standardized uptake value (SUV) ratio of tumor/liver less than or equal to 1

PR = decrease in SUV ratio of tumor/liver (at least 30%) PD = increase in SUV ratio of tumor/liver (at least 20%)

SD = no significant change in SUV ratio of tumor/liver

Local tumor progression will be defined as $\geq 20\%$ increased size on CT scan compared to a CT scan from prior to treatment. Distant progression will be defined as any new tumor found outside of the pancreas or periampullary region on CT scan. Local and/or distant progression by both PET (if available) and CT scan will be recorded separately. We will also determine PET response with the new PERCIST criteria as reported by Wahl et al. (J Nuc Med 2009; 50:122S-150S).

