11.1.3 Methods for Evaluation of Measurable Disease

Pancreas protocol CT scans (biphasic imaging, 1.25 mm cuts) and/or FDG PET-CT scans (optional and if recommended by the treating physician) will be obtained at all follow-up intervals as described in the treatment calendar.

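### Local progression is a 20% increase on CT with no millimetre minimum and no confirmation, so in small stable lesions reading error alone can count as an LPFS event

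*Combined protocol and SAP*

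**What the plan says.** - **Size at entry (4.1.4).** "Pancreatic or periampullary tumors must be less than 8.0 cm in greatest axial dimension at the time of treatment planning". No criterion in section 4 sets a minimum size or asks for a measurable lesion. Where histology cannot be obtained, 4.1.3.2 accepts "a rising CA 19-9 or radiographic evidence of recurrence on MRI, CT, and/or PET scan", so raised marker levels can stand in for imaging evidence.
- **Progression rule (11.1.2).** Local progression is 20% or greater "increased size on CT scan compared to a CT scan from prior to treatment". The response list in the same section words the threshold differently: "PD = more than 20% increase in the longest diameter of the index lesion". Neither gives an absolute increase or asks for confirmation.
- **Reference scan (11.1).** "All subsequent scans (post-treatment) will be compared to the same pretreatment CT or PET/CT that was used in conjunction with radiation treatment planning". The reference is fixed at baseline and is not the smallest later value.
- **Looks (11.1.3 and the section 10 calendar).** Scans "will be obtained at all follow-up intervals as described in the treatment calendar": months 4, 6, 9 and 12 in year 1, plus a conditional scan at 4-6 weeks.
- **Use.** LPFS counts local/regional progression or death (13.6). It carries stated power of 89% and 90% (13.4.2) and a cohort halt (12.2, 13.5). It is a secondary endpoint.

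**The concern.** A purely relative threshold shrinks with the lesion. A 20% increase is 2 mm at 10 mm, 3 mm at 15 mm and 4 mm at 20 mm, which may lie within reading error. The rule is applied at each scheduled scan and one crossing is enough, so false calls accumulate over the year.

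Small lesions are plausible, because both cohorts admit resected patients with local recurrence. If enough of them enrol, observed LPFS falls towards the null values, the estimated incidence of local progression in the competing-risk analysis rises, and the result depends partly on the mix of lesion sizes.

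**Working it through.** **1. The plan's own power figure.** Inputs from 13.4.2: n = 60 per cohort, one-sided alpha 0.04 (z = 1.751), exponential times, 2.5-year uniform accrual, 1-year follow-up. With λ = −ln(1-year LPFS):

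D = 60 × [1 − (e^(−λ) − e^(−3.5λ)) / (2.5λ)]

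Power = Φ{[ln(λ0/λ1) − 1.751/√D0] × √D1}

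- Cohort A (30% to 45%): λ0 = 1.204, λ1 = 0.799, D0 = 54.3, D1 = 48.3; power 88.6% (stated 89%).
- Cohort B (50% to 65%): λ0 = 0.693, λ1 = 0.431, D0 = 45.7, D1 = 36.1; power 90.4% (stated 90%).

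The stated figures reproduce.

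**2. False progression in an unchanged lesion.** Assumptions, none of them in the documents: true diameter d constant, independent normal reading error with SD s at baseline (B) and at each follow-up (F), four follow-up scans. A scan is called progression if F ≥ 1.2B. For one scan the chance is Φ(−0.2d / (s√2.44)), because F − 1.2B has mean −0.2d and variance s²(1 + 1.44). At 15 mm this is 2.7% for s = 1 mm and 16.8% for s = 2 mm. The chance of at least one crossing in four scans comes from simulation (400,000 draws), since the scans share one baseline reading:

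| Lesion | 20% equals | SD 0.5 mm | SD 1 mm | SD 2 mm | SD 2 mm, strict 5 mm minimum |
|---|---|---|---|---|---|
| 10 mm | 2 mm | 1.7% | 24% | 51% | 11% |
| 15 mm | 3 mm | 0% | 8% | 37% | 11% |
| 20 mm | 4 mm | 0% | 1.7% | 24% | 11% |
| 30 mm | 6 mm | 0% | 0% | 8% | 8% |
| 40 mm | 8 mm | 0% | 0% | 1.7% | 1.7% |

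Only the ratio d/s matters without a minimum, hence the repeated 24%. From 25 mm upwards 20% is already 5 mm, so the minimum does almost nothing there.

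**3. Lesions that shrink.** With a true 30% decrease and SD 1.5 mm, the four-scan rate falls from 24% to about 0.3% at 15 mm and from 1.7% to 0% at 30 mm.

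**4. Effect on LPFS and power.** If a fraction q of otherwise event-free patients is falsely called, observed 1-year LPFS = target × (1 − q). Putting that value into the power formula in step 1:

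| q | Example giving this q | LPFS A / B | Power A / B |
|---|---|---|---|
| 0% | none | 45% / 65% | 89% / 90% |
| 2% | mix below, strict 5 mm minimum | 44% / 64% | 85% / 85% |
| 5% | mix below, 5 mm minimum plus confirmation clause | 43% / 62% | 78% / 74% |
| 6.5% | mix below, half of event-free lesions shrink 30% | 42% / 61% | 74% / 67% |
| 13% | equal 15 mm and 30 mm lesions, SD 1.5 mm, all unchanged: (24% + 1.7%)/2 | 39% / 57% | 54% / 34% |

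The 5% counts confirmations only within the four scans, so it is slightly low.

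**5. Interim halt.** Taking 16 patients per cohort and an exact binomial interval as a simplification of the Kaplan-Meier one, the upper 98% bound is below 30% only with 0 of 16 event-free (1 − 0.01^(1/16) = 25%), and below 50% only with at most 2 of 16. In cohort A the halt probability moves from 0.55^16 = 0.01% to 0.61^16 = 0.04%. In cohort B it moves from 0.002% at 65% to 0.03% at 57%.

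**The case against.** The strongest reply is that no bias has been shown. The documents give no lesion-size distribution and no reading error, and at SD 0.5 mm, or if most lesions are 40 mm or larger, the effect is negligible. The fixed baseline protects responders: the earlier 33 Gy trial summarised in 3.3 reported response in 41% and stable disease in 41%, so about half of its non-progressors had shrunk. The same baseline works in the other direction too, because regrowth after shrinkage is not progression until it exceeds the pre-treatment size by 20%, which raises LPFS. Section 11.1.3 specifies 1.25 mm cuts, and 11.1.7 provides independent radiology review, image review by the investigator and simultaneous chart review.

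Most of this stands, and it limits the conclusion to stable small lesions. The quality safeguards help less than they seem to. The calendar footnotes allow chest/abdomen/pelvis CT and local evaluations, and the independent reader applies the same threshold without a minimum.

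A reader might infer several stronger points that the documents do not support:
- **LPFS is biased downward overall.** The two effects oppose each other and neither can be sized from the documents.
- **The stated power is wrong.** It reproduces. The 54%/34% is one scenario in which half of the lesions are 15 mm and none shrinks.
- **A cohort could be halted wrongly.** The halt probability stays below 0.1% even in that scenario.
- **The protocol concedes that the CT call is unreliable.** Section 8.2.1.3 asks how far "dynamic PET can be used to aid in the discrimination of tumor from radiation induced inflammation", but that sub-study concerns FDG uptake at baseline and on day 5 of treatment, not CT diameter at 4-12 months.
- **Criterion 4.1.4 is defective.** The gap is in the progression rule.

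**Conclusion.** The concern holds in conditional form. Section 11.1.2 lets a 2-4 mm reading difference count as local progression in a stable lesion of 10-20 mm, and nothing at entry keeps such lesions out. For those lesions the direction is towards lower LPFS. The size runs from negligible to material and rests on assumed values: reading SD of 1-2 mm, independent errors, four scans and an unchanged tumour. Net cohort bias is not established. No stated figure is wrong, the interim halt is practically unaffected, and the primary toxicity endpoint and its two-stage rule are untouched. The change is still worth making, because LPFS is the stated measure of efficacy in 13.6 and carries its own power claim, and the rule is cheap to tighten.

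**What to change.** In 11.1.2, define local progression as an increase in longest diameter of at least 20% **and** at least 5 mm over the pre-treatment CT. An increase of 20% or more but below 5 mm counts only if the next scheduled scan confirms it, and is then dated to the first scan. Carry this into LPFS, PFS and the competing-risk analysis. Use one threshold wording in both places in 11.1.2, where the text now says 20% or greater in one and more than 20% in the other. Record the baseline longest diameter, so that the share of small lesions can be reported. Criterion 4.1.4 needs no change.

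The cost is wording only, with no added scan or reader. There are two drawbacks. True progression in lesions under 25 mm may be confirmed one scan later, which back-dating largely offsets. Some false calls also remain: about 5% instead of 13% in the equal 15/30 mm mix at SD 1.5 mm, and about 11% at SD 2 mm for lesions of 20 mm or less even with a strict minimum. The confirmation clause raises that last figure somewhat, in exchange for not missing small true increases.
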